#### **b. Inclusion and Exclusion Criteria**

#### **Aim 1: Co-create plans for optimizing Measurement Based Care (MBC) implementation for youth with comorbidities.**

Clinic staff/Therapists (N=78) across 4 CMHCs in Washington state.

Inclusion: Must be aged 21+ and be working at a CMHC that is participating in the WA State CBT (Cognitive Behavioral Therapy) + Initiative.

Exclusion: Must be willing to participate in study activities.

#### Youth (N=22)

Inclusion: aged 13-17 years, receiving treatment at CMHC participating in the WA State CBT (Cognitive Behavioral Therapy) + Initiative.

Exclusions: youth who are suicidal, psychotic, not cognitively able to safely participate in MBC, and not able to read and write in English.

#### **Aim 2: Compare MBC fidelity post IMPACT Center methods deployment versus historical controls.**

Clinic staff/Therapists (N=30; subset of 78 clinic staff/therapists in Aim 1) across 4 CMHCs in Washington state.

Inclusion: Must be aged 21+ and be working at a CMHC that is participating in the WA State CBT (Cognitive Behavioral Therapy) + Initiative.

Exclusion: Must be willing to participate in study activities

Youth: NA, there are no Youth Participants in this aim

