#### Therapists/Clinic Staff:

Rapid Ethnographic Assessment Interviews – 120 participants

Design Kit – 32 participants (subset of the 120 interviewed)

Barrier Prioritization – 24 participants (subset of 120 interviewed)

Causal Pathway Diagramming – 20 participants (subset of 120 interviewed)

Focus Groups to improve IMPACT methods– 20 participants (subset of 120 interviewed)

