### AIM 2: Compare MBC fidelity post IMPACT Center methods deployment versus historical controls (not associated with a site visit)

NIMBLE will compare data at a clinic level prior to MBC training and at 6- and 18-months post site visit 1.

Our approach is to evaluate, at a clinic level, use of MBC before and after IMPACT method deployment. Specifically, we focus on whether therapists engaged in the main components of MBC: (1) Collect, or how often measures were provided to patients (frequency of administration), (2) Share, or how often therapists discuss outcome measures with their patients, and (3) Act, or whether therapists and patients used outcome measure data to change their direction in therapy (reevaluation using data).

We will use two different methods to assess use of MBC. The first is a short anonymous self-report survey filled out before implementing new strategies to address barriers to MBC use, and a second time 6 months after implementation. The second method is to ask for 5 therapists to enter data from 5 cases related to MBC use into the Washington State CBT+ Dashboard. Data will be aggregated at the clinic level, as we are investigating whether IMPACT methods impact clinic-wide changes. We are not studying whether any individual person's behavior changes as a result of IMPACT methods.

Clinic staff/Therapists (N=30) across 4 CMHCs in Washington state.

Inclusion: Must be aged 21+ and be working at a CMHC that is participating in the WA State CBT (Cognitive Behavioral Therapy) + Initiative.

Exclusion: Must be willing to participate in study activities

Youth participants: NA, there are no Youth Participants in this aim

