**AIM 2: Compare MBC fidelity post IMPACT Center methods deployment versus historical controls**

Clinic Staff/Therapists: At the end of each Aim 1 interview with clinic staff, we will ask them whether

they would be willing to participate in data collection efforts for Aim 2. We will provide the clinic staff

information sheet. Therapists will already be familiar with this process as they do this as part of standard clinic training.

Youth identification: NA, no youth activities

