Historical data has already been collected and is available to the study team as part of their involvement in the CBT+ initiative and ongoing practice improvement work. As part of

their clinic training, each therapist in these clinics participates in a CBT+ training. For the training, they track MBC data for up to 5 cases. To log the data for these 5 cases, therapists log into an account set up for them by an administrator and enter the data under a pseudonym. They can choose any code (e.g., “Marty McFly”) to identify their patient so long as it does not contain the name of their patient or any other identifying information. Thus, all client-level data are de-identified before they are entered into the system. While administrators have access to website data that contains therapist names and other information, that information is not and will not be accessible to this study team.

For post-IMPACT comparison data, therapists providing data will fall into two categories. The first category are therapists who have not gone through the CBT+ training yet. These therapists will follow the same procedures as those who entered historical data. The second category are therapists who have already completed their CBT+ training. We will ask the second category therapists to track data for 5-8 new cases. They will go through the same procedure as the other therapists with one exception. Rather than creating codes to identify patients themselves, our study team will have each therapist select a paper list of up to 8 identifying codes (e.g., AA1, AA2...AA8) to use to identify their patients. We will not keep any document that links any specific codes to any therapist. In this way, we will be able to isolate data identified by those codes, and identify that they came from a therapist within a specific clinic, but we will not be able to identify therapists individually.

**Data Collection Instruments** (these documents have all been uploaded to IRBNet:

Clinic Site Visit interviews: Supervisor-level interview guide, Management-level interview guide, Clinician-level interview guide, Admin Support Interview guide, AIM FIM IAM measures, and Implementation Climate Scale.

NIMBLE Youth Design Kits: Youth Design Kit Instructions, Youth Activity Cards, Follow-up design kit interview.

NIMBLE Clinician Design Kit: Clinician Design Kit Instructions, Clinician Activity Cards, Follow-up design kit interview.

Implementation outcome scale (AIM FIM IAM measures.docx) – Package 1

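### As the protocol describes Aim 2 recruitment, the clinic-wide fidelity conclusion rests on volunteers, with no response denominator and an unknown share of implementation-team members

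*Protocol*

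**What the plan says.** The target is the clinic. Section 5a of the protocol, under Aim 2, states: "Data will be aggregated at the clinic level, as we are investigating whether IMPACT methods impact clinic-wide changes".

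The respondents are described more narrowly. Section 5b, Aim 2, gives "Clinic staff/Therapists (N=30; subset of 78 clinic staff/therapists in Aim 1) across 4 CMHCs in Washington state". Section 7a gives the only stated route into Aim 2: "At the end of each Aim 1 interview with clinic staff, we will ask them whether" they will take part. Section 8a places those interviews at site visit 1.

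Other passages are wider. Section 8a asks therapists in general to complete the anonymous survey. The SAP update says a form went to providers and attaches no Aim 1 condition. The inclusion criteria listed in Section 5b are only a minimum age and employment at a participating clinic; the subset condition stands beside the N.

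Section 4 also plans a clinic health-record dataset with no volunteer restriction. The updated analysis in the SAP uses provider self-report alone: a repeated-measures ANOVA over three time points, with last observation carried forward. Neither document states how many people are invited, or how respondents who sat on an implementation team will be identified.

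**The concern.** If Sections 5b and 7a govern, a therapist who declined the interview, or who joined the clinic after site visit 1, is not reached by the stated route. Those who are reached have already volunteered once. A before-and-after change among volunteers need not equal the change across the clinic, and there is no concurrent control arm against which to judge it.

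Implementation-team membership adds to this. Team members rank the barriers, build the causal pathway diagrams (Section 8a) and are contacted every two weeks about strategy deployment (Section 2b). They may then report on their own fidelity. Nothing in the plan excludes them, counts them or shows results without them. Because the protocol makes the survey anonymous, membership cannot be recovered later unless the form asks for it. Without a denominator, a reader of the results could not tell whether the respondents are most of the therapists or a small part of them.

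**Working it through.** **The plan's own figure.** The documents give no derivation of N=30. Section 2c asks for at least 5 therapists per clinic. 5 × 6 clinics = 30, which agrees with the six clinics in Sections 2a and 4. 5 × 4 clinics = 20, which does not agree with the four clinics in Section 5b. The source pool is also unsettled: Section 5b has "Clinic staff/Therapists (N=78) across 4 CMHCs in Washington state" and Section 5a has "Rapid Ethnographic Assessment Interviews – 120 participants". Up to 30 interviews per clinic (Section 8a) × 4 = 120, not 78. These counts matter because they set any denominator.

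**Step 1. Who is asked?**

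| Place | Who |
|---|---|
| Section 5b, Aim 2 | 30 of the 78 Aim 1 staff |
| Section 7a, Aim 2 | staff who gave an Aim 1 interview |
| Section 8a, survey | therapists, no Aim 1 condition |
| SAP update | providers, no Aim 1 condition |

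The first two rows cannot both hold with the last two unless one pair is taken to govern.

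**Step 2. How many of the 30 could be team members?** Inputs: n = 30 respondents; pool N = 78 (Section 5b) or 120 (Section 5a); team K = 24 for prioritization or 20 for diagramming (Section 5a), or 8 × 4 = 32 at the top of the 5 to 8 per clinic in Section 8a. Minimum = max(0, n − (N − K)). Maximum = min(n, K). Expected under a random draw = nK/N.

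| N | K | Minimum | Maximum | Expected |
|---|---|---|---|---|
| 78 | 20 | 0 | 20 | 30 × 20/78 = 7.7 (26%) |
| 78 | 24 | 0 | 24 | 30 × 24/78 = 9.2 (31%) |
| 78 | 32 | 0 | 30 | 30 × 32/78 = 12.3 (41%) |
| 120 | 24 | 0 | 24 | 30 × 24/120 = 6.0 (20%) |

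With the stated team of 24, at least 30 − 24 = 6 respondents cannot be prioritization participants.

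**Step 3. What would overlap do to the estimate?** Let s be the team share among respondents, w the team share in the pool, and g_T and g_O the mean gains of team members and others. The reported gain is s·g_T + (1 − s)·g_O and the pool gain is w·g_T + (1 − w)·g_O. The difference is (s − w)(g_T − g_O). With 24 of 78, w = 0.31 and s lies between 0 and 24/30 = 0.80, so s − w lies between −0.31 and +0.49. The difference is zero if the respondents are representative of the pool (s = w) or if the gains are equal. The documents give no value for g_T − g_O, so the calculation stops here. It also covers only team membership within the Aim 1 pool. For therapists outside that pool there is no roster count to work from.

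**The case against.** The strongest reply is that Section 7a was written for another task. It adds: "Therapists will already be familiar with this process as they do this as part of standard clinic training". That describes entering cases in the CBT+ dashboard, which the SAP update says was abandoned for lack of recruits. On that reading the survey never had an interview-only route. This has force, but Section 7a words its invitation for Aim 2 as a whole, Section 5b still sets the subset condition, and no other route is given. The reply shows that the text needs reconciling; it does not show who was invited.

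Second, the Aim 1 pool is broad. Section 8a has the team try to interview all clinic staff, so being an Aim 1 participant is a weak filter if most agree. That stands. A reader might infer that the 30 are the people who designed the strategies, because 30/4 = 7.5 per clinic is close to a team of 5 to 8. Similar group sizes do not show that the same people are in both, and no passage links them.

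Third, Section 8a says "each therapist in these clinics participates in a CBT+ training", from which a reader might infer that the post-IMPACT group is more selected than the historical one. The updated SAP no longer makes that comparison. It follows provider self-report over three time points, so volunteer selection applies at baseline too. What remains is a limit on generalizing to the clinic.

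Fourth, this is a pilot and some forms have evidently gone out, so an amendment may not reach all waves. That is fair and limits the remedy.

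**Conclusion.** The documents conflict on who may respond. Under Sections 5b and 7a, the self-reported fidelity sample is volunteer-selected and includes implementation-team members to an unknown degree: 0 to 24 of 30 with the Section 5a team, about 9 under a random draw from 78. The 24 and the 78 come from different sections, and the range assumes that they describe the same staff. If the upper team size in Section 8a is used instead, the ceiling is all 30.

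The size of any bias cannot be derived. Inflation is plausible if team members gain more and are over-represented, but a multiple of the true effect would need assumed gains that the documents do not supply, and a representative draw would give no bias from overlap at all. The point merits a change because the conclusion is clinic-wide and uncontrolled, the plan gives no means of detecting the problem, the health-record source that could offset it is absent from the updated SAP, and the remedy is cheap.

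**What to change.** 1. Reconcile the passages: remove the condition in Section 5b that Aim 2 staff come from the 78 in Aim 1, and state in Section 7a that the interview invitation is not the route into the survey. Settle 78 against 120 and four clinics against six.
2. Invite every therapist on each clinic's current roster at each wave, or at each wave still to come.
3. Report numbers invited and responding by clinic and wave.
4. Add one yes/no item on implementation-team membership. Show results with and without team members, pooled across clinics only, because with about 7 or 8 respondents per clinic a clinic-level split could identify people.
5. If collection is complete, report the denominator, limit the conclusion to respondents, and add the Section 4 health-record data to the SAP if it was obtained.

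The cost is a protocol amendment, one survey item and a roster count from each clinic. The apparent response rate will be lower and the observed effect may be smaller. Later joiners will have no baseline and cannot enter the repeated-measures ANOVA as written, since there is no earlier value to carry forward; the SAP should say how their responses will be reported.

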#### **c. Vulnerable Populations**

The only vulnerable population we will include is Children 13-17 years of age since the study focuses on improving mental health outcomes for this population. Children must have the ability to read and write in English, given the nature of the research methods.

#### **d. Potentially Vulnerable Populations**

N/A

## 6. Setting

This study was originally being done completely through KPWHR. [name], the scientific lead and site PI changed institutions to Brown University and continued his role as scientific lead. At KPWHR, [name] is the new site PI. All study activities will be done at KPWHR and Brown University. [name] will be engaged in all study activities (recruitment, providing study information sheet, interviewing, communicating with clinics, etc.). An IAA is under preparation between Brown University and KPILRB.

The research will be conducted in Community Mental Health Clinics in Richland and Yakima, Washington, as well as other clinics in the Puget Sound area of Washington state, with **all clinics being part of the Washington State CBT+ Initiative**. The Washington State CBT+ initiative (called **CBT+**) provides an ideal backdrop for conducting this work. CBT+ is an academic-community partnership funded by the state's Division of Behavioral Health and Recovery. Over nearly 15 years, the initiative has provided clinician training and some organizational support for delivering EBPs for children and adolescents in public mental health, with high practice community collaboration and leadership.

## 7. Recruitment & Consent

### a. Recruitment & Screening

Recruitment will happen in Washington State only, but [name] will be involved with recruitment of clinics and participants while at Brown University. All study activities will be done on a KP-provided computer. See section 9f for more information.

#### **Aim 1: Co-create plans for optimizing Measurement Based Care (MBC) implementation for youth with comorbidities.**

##### **Clinic Staff/Therapists:**

We will host a 2-hour kick-off meeting (in person or virtual) at all 4 clinics where study activities will be described, and clinic staff/therapists will have an opportunity to ask questions. We will provide NIMBLE Study Team contact information for any person who would like to ask questions individually.

##### **A1b: Rapid Ethnographic Assessment (REA) observations and interviews**

At the end of the workshop the co-investigators will describe the other components in the study and give or email clinic staff and therapists an information sheet detailing the opportunity to volunteer as participants in interviews and observations. Clinic staff/therapists who do not want to participate will not be included in the REA observation and will not be approached for a 1-time interview.

##### **A1c: Design Kit activity**

Therapists: We will provide a physical or emailed clinic staff information sheet detailing the design kit activity and ask for volunteer therapists at each clinic to participate.

Youth identification: Front desk at clinics will share a recruitment card attached with youth clients (aged

13-17) being seen at each clinic, and youth will call the study team if interested in participating. The recruitment card will contain study team contact information so that interested youth can call the study team to get more information and have a chance to ask questions about what study activities include. Once all questions have been answered and the participant has decided to participate, the assent process will be conducted over the phone with NIMBLE study investigator [name] or NIMBLE study project manager [name]. If the youth does not have the Youth Design Kit information sheet with them, we would ask for their email address and email a message with a vague subject title to them so we could look at it in real time as we discuss the design kit activity. Since youth will call us to participate, we do not feel there is undue influence or coercion from receiving the recruitment card at the therapist office. The recruitment card and information sheet can be taken home to share with parents if the youth wish to share their participation with their parents.

**A1d: Barrier Prioritization, A1e: Causal Pathway Diagramming, and A1f: Focus groups**

The clinic staff information sheet explains each of these additional activities.

At the first site visit we will ask clinic staff to provide their email addresses to us and tell us if they may be interested in participating in one, two or all three of these activities. One month before each activity, we will send clinic staff a reminder email with the information sheet, asking them to contact us if they are willing to participate. We will provide the interview guides/agendas to IRB for each activity with a modification prior to carrying out these activities.

**AIM 2: Compare MBC fidelity post IMPACT Center methods deployment versus historical controls**

Clinic Staff/Therapists: At the end of each Aim 1 interview with clinic staff, we will ask them whether

they would be willing to participate in data collection efforts for Aim 2. We will provide the clinic staff

information sheet. Therapists will already be familiar with this process as they do this as part of standard clinic training.

Youth identification: NA, no youth activities

**b. Informed Consent Process**

Consent and Waiver Table		
Population	Study Activity/Activities	Consent/Waiver Type
NIMBLE participants	Identification Study Enrollment	 Signed Consent Form  Waiver of Signed Consent (oral consent, information statement)

**Clinic Staff and Therapist Consent Process**

The NIMBLE team at KPWHRI and Brown University will begin the consent process on the initial visit to each CMHC. The first activity in the visit is a training workshop which focuses on the importance of MBC. This workshop is desired by each of the CHMC and leadership at each CHMC have deemed this a required workshop for all staff providing clinical services to youth. Of note, even though the MBC workshop is mandatory for therapists, the rest of the study activities are not. The study team will elicit questions and ensure that all staff and therapists understand what participation entails. To minimize the possibility of coercion or undue influence, the study team will ask those interested in learning more to remain in the room, while those not interested will be asked to leave, at which point the study team will complete the oral consenting process there. Over the course of the study, the team will revisit the activities with participants and make sure they still are comfortable participating. For in-person site visits to ensure that staff and therapists are comfortable with our team's presence in the clinic during clinic observation activities we will implement the following procedures:

1. Announce that the meeting/huddle is being observed at the start of the meeting. Explain what type of information will be noted as part of the observation (i.e., workflows, relationships, direct anonymized quotes, etc.). Give people the opportunity to “opt-out” at the earliest possible time in the meeting/huddle.
2. Putting a sign on the door or in the room, or both, explaining that this meeting is being observed as part of an ethnographic study. Notes are being taken about MBC topics. If you would prefer to not be included in the notes, please contact study team member ([name] or [name]) (will provide photos of team members). This ensures people that came in late are aware they are part of a study and know how to opt out.
3. Remind folks at the end of the meeting that this session was observed, and notes made about MBC specific topics, and how to opt out.

**c. Justification: Waiver of Informed Consent**

N/A

**d. Justification: Waiver of Signed Informed Consent**

The research involves no more than minimal risk to participants and involves no procedures for which written consent is normally required outside of the research context.

For youth, there is no in-person contact planned with the study team; it is only by phone.

**e. Limited English Proficiency Participants**

N/A

**f. Assent of Children and Parent Permission**

Youth will assent for participation in this research.

Youth clients receiving care at participating CMHCs will receive a recruitment information card and information sheet from the front desk of the clinic upon check-in, with a phone number to call if they are interested in participating.

We are requesting a waiver of parental consent because per WA State law, youth aged 13+ are permitted to access mental health services without parental consent or knowledge. Given this legal framework, and the study focus on youth mental health within the Community Mental Health Clinics, we will have youth assent process.

**g. Adults Unable to Consent/Decisionally Impaired**

N/A

**h. HIPAA Privacy Rule Authorization**

N/A

**i. Justification: Waiver or Alteration of HIPAA Privacy Rule Authorization**

N/A

